In order to determine whether the target response rate (p_1) is likely, an initial number of evaluable subjects (n_1 subjects) treated at the MTD or PAD and schedule of INCAGN01876 within the corresponding doublet or triplet expansion cohort will be enrolled in a cohort (Stage 1). If there are r_1 or fewer responses in the cohort, it will be concluded that the true response rate is unlikely to be greater than or equal to the target rate, and no more subjects will be enrolled in that tumor type in Stage 2. In the cohorts in which greater than r_1 responses are observed among the Stage 1 subjects, n_2 additional evaluable subjects will be treated in Stage 2 to estimate the response rate. At the end of Stage 2, if $\leq r$ subjects have responded among the n evaluable subjects, the doublet or triplet schedule will be declared nonpromising for that cohort.

In other words, after the study is finished, if there is a sufficient number of responses in the 2 stages combined, the study doublet or triplet is considered promising; otherwise it is considered nonpromising. The detailed calculations for each tumor type-specific doublet and triplet cohort are based on a 1-sided Type I error of 0.05 and power of 85%. The individual p_0 and p_1 values for the tumor types within doublet or triplet expansion cohorts are listed in Table 19.

For the PD-1 refractory SCCHN cohort in Treatment Group F, a Simon 2-stage design with an expansion stage, as summarized in Table 20, will be used. The definitions of p_0 , p_1 , r_1 , n_1 , and n_2 are the same as those in Table 19. At the end of Stage 2, if r_2 or fewer responses are observed in $n_1 + n_2$ subjects, the PD-1 refractory SCCHN cohort will be terminated early for futility. If more than r_2 responders are observed, an additional n_3 evaluable subjects will be enrolled in the expansion stage. At the end of the expansion stage, if $\leq r$ subjects have responded among the n evaluable subjects, the concurrent dosing strategy of INCAGN01876 and nivolumab will be declared nonpromising for the PD-1 refractory SCCHN cohort. In other words, after the study is finished, if there is a sufficient number of responses in the 3 stages combined, the doublet schedule of INCAGN01876 and nivolumab will be considered promising for the PD-1 refractory SCCHN cohort; otherwise it is considered nonpromising. With this 3-stage design, the 1-sided Type I error is 0.0231, and the power is approximately 88%.

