**Table 2: Planned Simon 2-Stage Designs for Phase 2**

Indication	Treatment Groups	$r_1$	$n_1$	$r$	$n_2$	$n$	$p_0$	$p_1$
SCCHN	F, G, H	3	16	10	30	46	15%	35%
Gastric	F, G, H	3	16	10	30	46	15%	35%
Endometrial	F, G, H	4	17	14	34	51	20%	40%
SCHHN	J, K, L	5	18	17	32	50	25%	45%
Gastric	J, K, L	5	18	17	32	50	25%	45%
Endometrial	J, K, L	7	21	19	27	48	30%	50%

- $r_1$ : if  $r_1$  or fewer responses are observed during Stage 1, the study cohort is stopped early for futility.
- $n_1$ : number of subjects initially enrolled in Stage 1.
- $n_2$ : number of subjects enrolled in Stage 2.
- $r$ : if  $r$  or fewer responses are observed by the end of Stage 2, then no further investigation of the drug combination is warranted in the selected tumor type and dosing schedule.
- $n$ : total number of subjects.
- $p_0$ : insufficient response rate.
- $p_1$ : target response rate.

In Phase 2 of the study, toxicities will continue to be monitored. If the cumulative incidence of Grade 3 to 5 INCAGN01876-related AEs occurs in > 40% of subjects in a particular treatment group after 6 subjects have been enrolled, then further enrollment in that treatment group will be interrupted until the sponsor, investigators, and regulatory authorities (if applicable) determine the appropriate course of action (eg, lower the dose of INCAGN01876, change dose frequency, etc). If a treatment group is discontinued due to toxicity, it may be re-initiated at a previously tested lower dose level and/or alternate dosing schedule. All AEs, regardless of the time of occurrence on study, may be considered for DLT determination purposes.

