### Simulations and Operating Characteristics

Computer simulations were conducted in R to compare the operating characteristics of the Bayesian basket trial design with the operating characteristics of 18 separate Simon 2-Stage designs. We investigated 6 scenarios that would represent different configurations of null and alternative hypotheses (corresponding to inactivity of drug and activity of drug) within the sequencing strategies and tumor types. For the global null hypothesis of no activity in any cohort (Scenario 1), 2500 replications were performed. All other scenario results were simulated using 1000 replications.

In the computer simulations, we assumed the prior probability of correlation between cohorts within tumor types and sequencing strategies to be  $\lambda = 0.4$  and prior probability of activity to be  $\gamma = 0.4$ .

The Simon 2-Stage designs used in the simulations are given in [Table 2](#). The  $p_1$  and  $p_0$  values are assumed not to change with sequencing strategy. For example, for each of the 3 sequencing strategies tested on the SCCHN doublet,  $p_1 = 0.35$  and  $p_0 = 0.15$ . The total sample sizes if each cohort reached full enrollment are given by the  $n$  column in [Table 2](#).

Within the simulations, a tumor-sequence pair  $(i, j)$  was stopped if neither  $PoS1_{ij}$  nor  $PoS2_{ij}$  was  $\geq 20\%$  at any point. In addition, the first stage rule for the Simon 2-stage design was also applied where enrollment was halted unless more than  $r_1$  of the first  $n_1$  subjects responded to treatment within a tumor-sequence pair. The method rejected the null hypothesis of no activity in a cohort at the end of the study if either  $PoS1_{ij}$  or  $PoS2_{ij} > 80\%$ .

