**Table B3: Operating Characteristics Based on Simulation Results**

Scenario	Expected Sample Size	Probability of a Single False Positive Result	Expected Number of False Positive Results	Power to Reject <math>\geq 1</math> True Alternative Hypothesis	Expected Number of True Rejections	Number of True Alternative Hypotheses	Expected Sample Size for Simon 2-Stage Design	Expected Number of Correct Rejections for Simon 2-Stage Design	Expected Number of False Rejections for Simon 2-Stage Design
Global null hypothesis	355.2	0.0876	0.104	–	–	0	457.2	–	0.9
Global alternative hypothesis	807.0	–	–	> 0.999	16.3	18	807.7	15.3	–
Alternative hypotheses in Tumor Type 1, null for Tumor Types 2 and 3	534.8	0.135	0.153	> 0.999	5.0	6	574.7	5.1	0.6
Alternative hypothesis in Sequence 1, null for Sequences 2 and 3	527.9	0.150	0.162	> 0.999	5.4	6	574.0	5.1	0.6
Alternative hypothesis in Tumor Type 1 in triplet, all others null	444.5	0.127	0.139	0.978	2.5	3	515.7	2.55	0.75
Alternative hypothesis in Tumor Type 1 in triplet Sequence 1, all others null	387.7	0.123	0.136	0.637	0.6	1	476.7	0.85	0.85

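### A cohort closed for futility at Stage 1 can still be declared successful on borrowed data, and the 16.3 of 18 true rejections in SAP Table B3 includes such cohorts

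*SAP*

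**What the plan says.** Two rules act on the same Phase 2 cohorts.

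The first is the Simon Stage 1 rule. For a cohort with r1 or fewer responses, Protocol 9.2.2 says that "it will be concluded that the true response rate is unlikely to be greater than or equal to the target rate", and it ends enrollment in that cohort. SAP 3.4.2 says the same, and SAP 9.1.2.1 discontinues the cohort. Appendix B confirms that the rule was part of the simulations: "the first stage rule for the Simon 2-stage design was also applied where enrollment was halted unless more than" the cutoff number of responses was seen in Stage 1.

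The second is the end-of-study Bayesian rule. In the simulations, "The method rejected the null hypothesis of no activity in a cohort at the end of the study if either" PoS, pooled within tumor type or within sequence, was above 80%. Earlier in Appendix B, after Table B1, and in Protocol 9.6.2, the same criterion defines success for the trial itself. None of the three statements mentions Stage 1.

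Table B3 reports, for the row "Global alternative hypothesis", 16.3 expected true rejections among 18 active cohorts and an expected sample size of 807.0; the separate Simon designs have 15.3 and 807.7. For "Alternative hypothesis in Sequence 1, null for Sequences 2 and 3" it reports 5.4 of 6 and 527.9, against 5.1 and 574.0. Every scenario except the global null used 1000 replications.

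**The concern.** Taken together, the rules allow two opposite conclusions about one cohort: closed as inactive after Stage 1, then declared successful because other cohorts in the same sequence or tumor type did well. The documents do not say which conclusion stands. The halted cohort adds no subjects, so only results from other cohorts can move its PoS after that.

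Two things depend on this. One is what may be called successful in the final report, because Protocol 9.6.2 is current text. The other is the operating characteristics: if the simulation counted such cohorts as true rejections, that column of Table B3 includes outcomes that the Stage 1 rule does not permit.

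**Working it through.** **1. Inputs, and the plan's own figures reproduced.** From SAP Table 2, with X ~ Binomial(n1, p1), P(pass Stage 1) = P(X > r1):

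| Design (three sequences each) | r1/n1 | p1 | P(pass) |
|---|---|---|---|
| Doublet SCCHN, doublet gastric | 3/16 | 35% | 0.8661 each |
| Doublet endometrial | 4/17 | 40% | 0.8740 |
| Triplet SCCHN, triplet gastric | 5/18 | 45% | 0.8923 each |
| Triplet endometrial | 7/21 | 50% | 0.9054 |

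The first entry agrees with SAP Table 11: 1 − 0.8661 = 13.4% early termination at a 35% response rate. With E[N] = n1 + P(pass) × n2, the 18 cohorts sum to 807.7 under the global alternative, 457.2 under the global null and 574.0 with Sequence 1 active, all as in Table B3. Exact Simon correct rejections are 15.32 and 5.11, against 15.3 and 5.1 in the table. The inputs are therefore the right ones.

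**2. Expected number passing Stage 1.** For one sequence: 2 × 0.8661 + 0.8740 + 2 × 0.8923 + 0.9054 = 5.296 of 6. For three sequences: 3 × 5.296 = 15.89 of 18. Suspension for low PoS can only lower these numbers, because it may keep a cohort from reaching n1. The Stage 1 rule was clearly in force: the expected size of 807.0 is close to Simon's 807.7 and well below the maximum of 3 × (46 + 46 + 51 + 50 + 50 + 48) = 873.

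**3. Monte Carlo error.** The variance of the number passing, per sequence and replication, is Σ P(1 − P) = 0.2319 + 0.1101 + 0.1922 + 0.0857 = 0.6199. Over 1000 replications the SE is √(3 × 0.6199/1000) = 0.043 for 18 cohorts and √(0.6199/1000) = 0.025 for six. Taking the smallest values that round to the printed ones:

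- Global alternative: (16.25 − 15.889)/0.0431 = 8.4 SE above.
- Sequence 1 active: (5.35 − 5.296)/0.0249 = 2.2 SE above.

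**4. Remaining rows.** Scenarios 3, 5 and 6 report 5.0, 2.5 and 0.6, below their bounds of about 5.3, 2.7 and 0.9. The bound shows nothing there.

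**5. Mechanism.** Take a doublet SCCHN cohort closed at 3/16. Its likelihood ratio, active to inactive, is (0.35/0.15)³ × (0.65/0.85)¹³ = 12.70 × 0.0306 = 0.388. Alone, with γ = 0.4, the odds are (0.4/0.6) × 0.388 = 0.26, so PoS is about 0.21. Now pool it with five other strata in its sequence that are clearly active (an illustrative assumption). The prior weight for all six active is 0.6 × 0.4⁶ + 0.4 × 0.4 = 0.1625. The prior weight for the other five active and this one inactive is 0.6 × 0.4⁵ × 0.6 = 0.00369. The ratio is 44.1, the odds are 44.1 × 0.388 = 17.1, and PoS is about 0.94, above the 80% threshold.

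**6. Re-simulation.** Two re-simulations followed Appendix B (λ = γ = 0.4, 16-week response delay, Table B2 accrual, re-opening allowed). With halted cohorts still eligible, they gave 16.3 and 16.38 true rejections for the global alternative, and 5.4 and 5.41 for Sequence 1. Of these, 0.81 and 0.70, and 0.27 and 0.25, were cohorts that had failed Stage 1. Excluding them leaves about 15.5 and 15.7, and 5.15 and 5.17. The second used 260 replications (SE 0.10 and 0.07) and paused accrual at n1 until Stage 1 was evaluable, which the SAP does not specify. Its expected sample sizes were 803 and 542, against 807.0 and 527.9 in Table B3, so the match is close but not exact.

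**The case against.** The best defence is that Appendix B discloses its success rule and Table B3 follows it. The 16.3 is then not an arithmetic error, and 15.89 is a ceiling only under a condition that Appendix B never imposes. Protocol 9.6.2 also presents the Bayesian analysis as a second approach to judging activity, so borrowing may be meant to count. The first part stands: the table reports the rule as written. It does not remove the conflict, because no passage says that borrowed data may overturn a Stage 1 stop.

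A practical objection also stands in part. Table B3 covers 18 cohorts, including endometrial cancer and Groups G and K, which the current protocol no longer has, and Amendment 5 states that enrollment is complete. A re-run cannot change accrual. The success rule, however, still governs what is reported.

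Two stronger readings are tempting. A reader might infer that the SAP claims a power advantage over separate Simon designs and that this advantage is mostly spurious. The text before Table B3 claims a smaller sample size, Type I error near 10% and high power. The power column concerns rejecting at least one true alternative. Three of the five rows with active cohorts show fewer true rejections than Simon (5.0 against 5.1, 2.5 against 2.55, 0.6 against 0.85).

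A reader might also infer that the Simon columns mix exact and nominal values, since 0.9 is 0.05 × 18 while the exact sum is 0.84. But 15.3 is equally 0.85 × 18, so both columns fit the design error rates and no inconsistency can be shown.

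**Conclusion.** The point holds as a conflict between rules that is visible in one published figure. In the global-alternative row, 16.3 true rejections cannot be reconciled with 15.89 cohorts expected to pass Stage 1, so the count includes cohorts that did not pass. The Sequence 1 row points the same way but is weak evidence alone. The other rows are uninformative.

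The affected quantity is the expected number of true rejections. The power to reject at least one true alternative would hardly change. The bound rests only on SAP Table 2, independent cohort outcomes at p1 and 1000 replications. It is an expectation, not a cap on any single trial. The corrected counts are less certain, because they depend on accrual-pause and re-opening details that the SAP does not give.

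**What to change.** Add one condition to the end-of-study success rule in both places in SAP Appendix B (after Table B1 and in the simulations section) and in Protocol 9.6.2: *and the cohort passed Stage 1, with more than r1 responders among its first n1 evaluable subjects*. The rule then agrees with Protocol 9.2.2 and SAP 3.4.2 and 9.1.2.1.

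Re-run Table B3 under that rule, including its false-positive columns, and carry the global-null row into SAP Table 13, which repeats it. Take the restated true-rejection counts from the re-run; roughly 15.5 to 15.7 of 18 and 5.15 to 5.2 of 6 can be expected. State the accrual-pause and re-opening assumptions with the results.

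The cost is one clause in three places and a re-run of existing code. The true-rejection column becomes slightly less favourable. No subjects or procedures are added.

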**Table B2: Simulated Enrollment by Quarter-Year From Trial Start**

Quarter #	1	2	3	4	5	6
Enrollment	28	76	136	207	284	369
Quarter #	7	8	9	10	11	
Enrollment	460	557	658	766	873	

The operating characteristics obtained from the simulations are given in [Table B3](#). Compared against 18 separate Simon 2-Stage designs, the Bayesian basket trial offers a significant reduction in sample size and close to 10% Type I error control. The individual Simon 2-Stage designs are considered to be independent trials and would offer no attempt to control Type I error. The Bayesian basket trial also offers high power (in most cases more than 97%) to reject the null hypotheses of no activity in the cohorts when activity is present. In Scenario 6, when only 1 of the 18 cohorts has activity, the Bayesian basket trial still has 63.7% power to reject the null hypothesis for that cohort.

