**Table 12: Bayesian Pooling Strategy by Tumor Type and Sequencing Strategy**

Dosing Schedule	Tumor Types Within Treatment Group		
	Endometrial	Gastric	SCCHN
Treatment Group F	1, 4	1, 5	1, 6
Treatment Group G	2, 4	2, 5	2, 6
Treatment Group H	3, 4	3, 5	3, 6
Treatment Group J	1, 7	1, 8	1, 9
Treatment Group K	2, 7	2, 8	2, 9
Treatment Group L	3, 7	3, 8	3, 9

- 1 = Concurrent dosing
- 2 = Run-in only dosing
- 3 = Run-in + concurrent dosing
- 4 = Endometrial within 1876 + Nivo
- 5 = Gastric within 1876 + Nivo
- 6 = SCCHN within 1876 + Nivo
- 7 = Endometrial within 1876 + Nivo + Ipi
- 8 = Gastric within 1876 + Nivo + Ipi
- 9 = SCCHN within 1876 + Nivo + Ipi

[Table 13](#) provides the operating characteristics for 1000 simulated clinical trials under the global null hypothesis, under which none of the 18 cohorts are active. The table summarizes the expected sample size, expected number of false rejections, and the probability of at least 1 false positive result (family wise error rate) for the integrated Bayesian analysis. For comparison purposes, the table summarizes the expected sample size, and expected number false rejections

for 18 separate Simon 2-stage designs in which the cohorts are stopped for futility according to only the Simon 2-stage rules. In the integrated Bayesian analysis, a cohort can be stopped for futility if either PoS1 or PoS2 is not  $\geq 20\%$  or because the cohort does not meet the response rate requirement of the Simon 2-stage rule at Stage 1. From the table, under the global null hypothesis and certain enrollment assumptions, the integrated Bayesian analysis will result in 22% fewer subjects on average.

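### SAP Appendix B misdescribes its Table B3: the power above 97% is for finding at least one active cohort, and family-wise error near 10% holds only under the global null

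*SAP*

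**What the plan says.** The summary is in SAP Appendix B, under Simulations and Operating Characteristics, in the paragraph after Table B2. Compared with 18 separate Simon designs, it says, the Bayesian design "offers a significant reduction in sample size and close to 10% Type I error control". It then claims "high power (in most cases more than 97%) to reject the null hypotheses of no activity in the cohorts when activity is present". The next sentence takes the scenario with one active cohort out of 18 and says that "the Bayesian basket trial still has 63.7% power to reject the null hypothesis for that cohort".

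The figures are in Table B3, "Operating Characteristics Based on Simulation Results", which covers six scenarios. One column gives the power to reject at least one true alternative. Separate columns give the expected number of true rejections and the number of true alternatives. The header of the false-positive column speaks of a single false positive. However, SAP Section 9.1.2.2 introduces the same 0.0876 in Table 13 as "the probability of at least 1 false positive result (family wise error rate) for the integrated Bayesian analysis". Table 13, in the main text, reports the global null only.

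SAP Section 3.4.2 sets each Simon design at one-sided 5% error and 85% power. Under Protocol Section 9.6.2 and SAP Appendix B, a tumor-sequence pair is a success if either PoS exceeds 80% at the end of the study.

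**The concern.** The PoS rule decides one tumor-sequence pair at a time, so per-cohort power is the property that tells a reader how to interpret a cohort's result. The sentence speaks of rejecting the null hypotheses in the cohorts, and a reader will take 97% as that property. It would then seem that the rule misses an active cohort about 3% of the time and comfortably beats the 85% of the Simon designs.

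Likewise, an unqualified Type I error close to 10% will be read as holding whichever cohorts are active. If either reading is wrong, the rule's stated properties are better than the simulated ones, and a cohort declared unsuccessful would carry more weight than it should.

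**Working it through.** **1. Check that Table B3 can be relied on.** For each Simon design in SAP Table 2, expected N = n1 + (1 − PET) × n2, where PET is the binomial probability of r1 or fewer responses among n1. For the SCCHN doublet at 15%, PET = 0.7899 (SAP Table 11 gives 79.0%), so expected N = 16 + 0.2101 × 30 = 22.30. The six designs give 22.30, 22.30, 25.22, 27.04, 27.04 and 28.48. Their sum times three sequences is 457.2, as in Table B3. Under the global alternative the same calculation gives 807.7, again as stated. The Simon correct rejections are 18 × 0.85 = 15.3, as stated.

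**2. Power.** Per-cohort power = expected true rejections ÷ number of true alternatives, all from Table B3. The Simon column gives 0.85 throughout (15.3/18, 5.1/6, 5.1/6, 2.55/3, 0.85/1).

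| Active cohorts | Power for at least one | True rejections ÷ active | Per-cohort power | Simon correct rejections |
|---|---|---|---|---|
| All 18 | >0.999 | 16.3/18 | 90.6% | 15.3 |
| Tumor Type 1 (6) | >0.999 | 5.0/6 | 83.3% | 5.1 |
| Sequence 1 (6) | >0.999 | 5.4/6 | 90.0% | 5.1 |
| Tumor Type 1 triplet (3) | 0.978 | 2.5/3 | 83.3% | 2.55 |
| One cohort | 0.637 | – | 63.7% | 0.85 |

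The only values above 97% are in the at-least-one column. No scenario reaches 97% per cohort; the miss rate is 9.4% to 16.7% in the first four rows and 36.3% in the last.

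Rejection counts are rounded to 0.1. So 5.0/6 lies between 4.95/6 = 82.5% and 5.05/6 = 84.2%, and 2.5/3 between 2.45/3 = 81.7% and 2.55/3 = 85.0%. These ranges cover rounding only. Monte Carlo error in the counts cannot be derived from the table, because cohorts in one simulated trial are correlated.

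**3. Family-wise error.** The 95% Monte Carlo interval is p ± 1.96 × √(p(1 − p)/N). Appendix B gives N = 2500 for the global null and 1000 for the other scenarios.

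| Scenario | Probability of at least one false positive | 95% interval |
|---|---|---|
| Global null | 0.0876 | 0.077–0.099 |
| Tumor Type 1 active | 0.135 | 0.114–0.156 |
| Sequence 1 active | 0.150 | 0.128–0.172 |
| Tumor Type 1 triplet active | 0.127 | 0.106–0.148 |
| One cohort active | 0.123 | 0.103–0.143 |

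All four mixed scenarios exclude 10% from below. (SAP Section 9.1.2.2 mentions 1000 trials for the global null. But 0.0876 × 2500 = 219 is a whole count and 0.0876 × 1000 = 87.6 is not, so 2500 fits.)

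**4. Context.** Per-cohort false-positive rate = expected false positives ÷ number of null cohorts: 0.104/18 = 0.6%, 0.153/12 = 1.3%, 0.162/12 = 1.35%, 0.139/15 = 0.9% and 0.136/17 = 0.8%. Eighteen independent 5% tests would give 1 − 0.95^18 = 60% family-wise.

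**5. Supporting simulation.** A separate simulation allowed suspended cohorts to reopen and paused enrollment at n1. It came within about 3 points of Table B3 on error and per-cohort power. With permanent stopping and no pause, power for the single active cohort fell to 0.49. The SAP is not explicit on these details, so nothing below rests on this simulation.

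**The case against.** No number in Appendix B is shown to be wrong. Table B3 labels the at-least-one column correctly and prints everything needed to derive per-cohort power. The 63.7% is stated openly in the same paragraph. The error sentence is a comparison with 18 separate Simon designs, and 12–15% is far below their roughly 60%; per-cohort error is also far below 5%. All of this stands. It makes the matter one of description, not of calculation or concealment.

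Several stronger readings are tempting, but the documents do not support them:

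- A reader might infer that the PoS rule breaks a promise of 85% power in three of five scenarios. The 85% is stated for the Simon designs, not for the PoS rule. One of the three values (2.5/3) is within rounding of 85%, and another (5.0/6) is only about 1 to 2.5 points short. The Bayesian design has more expected true rejections than Simon in two scenarios (16.3 against 15.3, and 5.4 against 5.1).
- A reader might infer that power drops below Simon whenever few cohorts are active. Two scenarios each have six active cohorts, one at 83% and the other at 90%, so the number active is not the whole explanation.
- A reader might infer that 12–15% breaches an error limit. SAP Section 3.3 and Protocol Section 9.3 control error per cohort and expressly make no allowance for multiple cohorts.

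The practical reach is also limited. The simulations cover 18 cohorts, including endometrial cancer and Groups G and K. The current protocol's Phase 2 groups no longer include these, and Amendment 5 records that enrollment is complete. Even so, Protocol Section 9.6.2 keeps the rule, and Appendix B is the fullest account of its operating characteristics in the two documents.

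**Conclusion.** The point holds as an error of description. The figure of more than 97% is true of detecting at least one active cohort in four of five scenarios. Power for a cohort in those four is about 83% to 91%, and it is 63.7% when only one cohort is active, as the text discloses. Error close to 10% is fair for the global null (0.0876). With some but not all cohorts active it is 0.123 to 0.150, at most 1.5 times the stated level.

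Against Simon's 85%, the Bayesian design is better in two scenarios, slightly lower in the two at 83% (one of them within rounding), and clearly lower with a single active cohort. There the 95% Monte Carlo interval is 0.637 ± 1.96 × √(0.637 × 0.363/1000), or 0.607 to 0.667.

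The conclusion rests on Table B3 as printed, on reading its false-positive column as at least one (as Table 13 does), and on the replication counts in Appendix B. It does not show the PoS rule to be unsuitable, and it changes no threshold or sample size.

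**What to change.** Replace the error and power claims after Table B2 in SAP Appendix B with text such as:

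> Family-wise error is about 9% under the global null and 12–15% when some but not all cohorts are active. The probability of detecting at least one active cohort exceeds 97% in four of five scenarios. Per-cohort power is 83–91% in those four and 64% when a single cohort is active, compared with about 85% for the separate Simon designs: higher than Simon in two scenarios, slightly lower in the two at 83% (the 2.5/3 value is within rounding of 85%), and clearly lower with a single active cohort.

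Add a per-cohort power column to Table B3. Relabel its false-positive column as the probability of at least one false positive, to agree with Table 13.

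The cost is a few lines of SAP text and one column obtained by dividing two existing ones. No simulation has to be rerun for this correction. The only downside is that the stated figures become less favourable.
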